## 3 OBJECTIVES AND ENDPOINTS

OBJECTIVES	ENDPOINTS	JUSTIFICATION FOR ENDPOINTS
Primary		

OBJECTIVES	ENDPOINTS	JUSTIFICATION FOR ENDPOINTS
Degree of Concordance Between Therapists' Feeding Therapy Recommendations	After reading a feeding case study, early intervention professionals will answer the question "Would you recommend feeding therapy?" with two choices: yes or no. Difference in agreement between early intervention professionals using the decision support tool and those not will be calculated and compared for cases A and B.	To determine whether using the tool, which helps identify feeding problem symptoms, changes decisions therapists make around recommending therapy for a child.
Degree of Concordance Between Therapists' Referral Recommendations	After reading a feeding case study, early intervention professionals will answer the question "Would you refer this family to any other providers/specialists for evaluation/treatment?" with two answer choices: yes or no. Difference in agreement between early intervention professionals using the decision support tool and those not will be calculated and compared for cases A and B.	To determine whether using the tool, which helps identify feeding problem symptoms by discipline with the explicit purpose of facilitating referrals, changes decisions therapists make around recommending referral to a specialist.
Degree of Concordance Between Therapists' Specific Specialist Referral Recommendations	After reading the feeding case study, early intervention professionals will answer the question "What other professionals would you refer this child to? Check all that apply." with the following choices: nutritionist/dietician, gastroenterologist, otolaryngologist (ENT), aerodigestive clinic, pulmonologist, occupational therapist, speech language pathologist, psychologist/social worker, applied behavior analyst (ABA), or allergist. Difference in agreement between early intervention professionals using the decision support tool and those not will be calculated and compared for cases A and B.	To determine whether the tool, which lists feeding problem symptoms by specialist discipline, changes the specialists a therapist refers to.
Secondary		

OBJECTIVES	ENDPOINTS	JUSTIFICATION FOR ENDPOINTS

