Degree of Concordance Between Therapists' Feeding Therapy Frequency Recommendations	After reading the feeding case study, early intervention professionals who recommended feeding therapy will answer the question "With what frequency would you recommend therapy?" with three choices: 2 times per week or more, 1 time per week, less than one time per week. Difference in agreement between early intervention professionals using the decision support tool and those not will be calculated and compared for cases A and B.	To determine whether using the tool, which helps identify feeding problem symptoms, changes decisions therapists make around recommending a specific frequency of therapy for a child.
Degree of Concordance Between Therapists' Intervention Target Choices	After reading the feeding case study, early intervention professionals who recommended feeding therapy will answer the question "What therapy targets might you include for this child?" and may check all that apply from the following choices: oral motor skills, sensory, behavioral, medication, modification of food/liquid, modification of equipment (seating, utensils, etc.), modification of environment (location, distractions, routine, etc.), parent coaching, or other. Difference in agreement between early intervention professionals using the decision support tool and those not will be calculated and compared for cases A and B.	To determine whether using the tool, which helps identify feeding problem symptoms by area of concern, changes decisions therapists make around recommending a specific intervention target for a child.
Decision Support Tool Acceptability Score	The Acceptability of Intervention Measure (AIM) will be used to measure acceptability of the decision support tool. This tool includes four items, rated on a five-point Likert scale from completely disagree to completely agree, and will be quantified with a score of 0 for completely disagree, 1 for disagree, 2 for neither agree nor disagree, 3 for agree, and 4 for completely agree. The average score across the four items will be calculated, with higher	To determine if this intervention is acceptable to practicing therapists.

OBJECTIVES	ENDPOINTS	JUSTIFICATION FOR ENDPOINTS

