## 4 STUDY DESIGN

### 4.1 OVERALL DESIGN

This is a randomized crossover pilot study. It will be conducted online through one site, UNC Chapel Hill. The study intervention is the 'Clinical Feeding Tool' also known as the decision support tool. Our hypothesis is that clinicians will change their recommendations for feeding therapy and specialist referral when using the tool compared to when they do not use the tool. Clinicians will be randomly assigned to respond to either Case A or Case B without using the tool (2 groups). Then, they will respond to the other case using the tool. Total participation time is estimated at 20 minutes.

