# 8 STUDY ASSESSMENTS AND PROCEDURES

## 8.1 EFFICACY ASSESSMENTS

To test intervention efficacy, the participant will be asked to answer a set of clinical questions after reading the case study. They will first do this without the intervention and then read another case study using the intervention. This will be administered through Qualtrics in survey form.

The questions include:

- Would you recommend feeding therapy to this child? Yes/No
  - If yes, "With what frequency would you recommend therapy?"
    - 2 times per week, 1 time per week, Less than one time per week
  - If yes, "What therapy target areas might you include for this child?" (select all that apply)

- Oral motor skills, sensory, behavioral, medication, modification of food/liquid, modification of equipment (seating, utensils, etc.), modification of environment (location, distractions, routine, etc), parent coaching, other (fill in)
- If yes, "What would be the recommended length of treatment for this child?"
  - Less than 6 months, 6-12 months, More than 12 months
- What diagnosis would you give this child?
- Would you refer this family to any other providers/specialists for evaluation/treatment? Yes/No
  - If yes, "What other professionals would you refer this child to? Check all that apply."
    - Nutritionist/dietician, gastroenterologist, otolaryngologist (ENT), aerodigestive clinic, pulmonologist, occupational therapist, speech language pathologist, psychologist/social worker, applied behavior analyst (ABA), allergist, multidisciplinary feeding team, other (list)

In addition to the clinical questions, the following questions will be asked in order for the participant to evaluate the tool:

- With a likert scale of completely agree, agree, neither agree nor disagree, disagree, completely disagree
  - The Clinical Feeding Guide meets my approval
  - The Clinical Feeding Guide is appealing to me
  - I like the Clinical Feeding Guide
  - I welcome the Clinical Feeding Guide
  - The Clinical Feeding Guide seems fitting
  - The Clinical Feeding Guide seems suitable
  - The Clinical Feeding Guide seems applicable
  - The Clinical Feeding Guide seems like a good match
  - The Clinical Feeding Guide seems implementable
  - The Clinical Feeding Guide seems possible
  - The Clinical Feeding Guide seems doable
  - The Clinical Feeding Guide seems easy to use
- If you could make changes to the CFG you would (check all that apply):

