### 9 STATISTICAL CONSIDERATIONS

#### 9.1 STATISTICAL HYPOTHESES

- Primary Efficacy Endpoint(s):
  - Degree of concordance between therapists’ feeding therapy recommendations
    - Null Hypothesis: There is no difference in therapists’ feeding therapy recommendations when using v. not using the tool

- Alternative Hypothesis: There is a difference in therapists' feeding therapy recommendations when using v. not using the tool
- Non-inferiority comparison
- Time period: After reading the case study
- Degree of concordance between therapists' referral recommendations
  - Null Hypothesis: There is no difference in therapists' referral recommendations when using v. not using the tool
  - Alternative Hypothesis: There is a difference in therapists' referral recommendations when using v. not using the tool
  - Non-inferiority comparison
  - Time period: After reading the case study
- Degree of concordance between therapists' specific specialist referral recommendations
  - Null Hypothesis: There is no difference in who the therapists recommend referral to when using v. not using the tool
  - Alternative Hypothesis: There is a difference in who the therapists recommend referral to when using v. not using the tool
  - Non-inferiority comparison
  - Time period: After reading the case study
- Secondary Efficacy Endpoint(s):
  - Degree of concordance between therapists' feeding therapy frequency recommendations
    - Null Hypothesis: There is no difference in therapists' feeding therapy frequency recommendations when using v. not using the tool
    - Alternative Hypothesis: There is a difference in therapists' feeding therapy frequency recommendations when using v. not using the tool
    - Non-inferiority comparison
    - Time period: After reading the case study
  - Degree of concordance between therapists' intervention target choices
    - Null Hypothesis: There is no difference in therapists' feeding therapy intervention target choices when using v. not using the tool
    - Alternative Hypothesis: There is a difference in therapists' feeding therapy intervention target choices when using v. not using the tool
    - Non-inferiority comparison
    - Time period: After reading the case study
  - Decision Support Tool Appropriateness
    - Null Hypothesis: The decision support tool is not appropriate.
    - Alternative Hypothesis: The decision support tool is appropriate.
    - Superiority
    - Time period: After using the tool

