### 9.4.3 ANALYSIS OF THE SECONDARY ENDPOINT(S)

For degree of concordance between therapists' feeding therapy frequency recommendations we have categorical data (2 groups – using and not using the tool; 3 response categories – 1xweek, 2xweek, less than 1 time per week). This is a repeated measure (therapists answer once for case A and once for case B). Each case will be analyzed separately. Due to the categorical data and small sample, reporting will be descriptive. Chi square tests will also be run if determined to meet the required assumptions. For chi-square tests, p value and effect size will be reported.

For degree of concordance between therapists' intervention target choices, descriptive statistics will be used due to the multiple categories (categorical data), small counts, and small sample size. The percentage of therapists recommending a particular provider will be compared among therapists using and not using the tool. This will be analyzed separately for case A and for case B.

For decision support tool acceptability, appropriateness, and feasibility, we have ordinal data (Likert scale). Additionally, each score (acceptability, appropriateness, feasibility) has 4 Likert scale items that form the score for that subscale. This is a single endpoint. The mean across the 4 items will be calculated for each participant to achieve a mean acceptability, appropriateness, and feasibility score. Then, the mean and standard deviation will be calculated across participants to result in an overall mean rating for acceptability, appropriateness, and feasibility.

Across all analyses, missing data will be reported but not corrected for due to the small sample size. Participants who did not complete all survey items will not be included in analysis. Adjustment for multiple comparisons is considered unnecessary due to the small sample size and minimal use of inferential statistics.

---

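### Therapy frequency is compared only among therapists who said yes to therapy, an answer the tool may itself change, so a shift in who says yes can look like, or hide, a shift in frequency

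*Combined protocol and SAP*

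**What the plan says.** The first primary endpoint in Section 3 is the yes/no answer to "Would you recommend feeding therapy". Section 4.1 gives the study hypothesis that "clinicians will change their recommendations for feeding therapy and specialist referral when using the tool".

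The secondary endpoints on frequency and on targets apply in Section 3 to "early intervention professionals who recommended feeding therapy will answer the question". The survey in Section 8.1 is built the same way: "With what frequency would you recommend therapy" and the target item both branch from a yes to therapy. The list of specialists branches from a yes to referral, which is another primary endpoint.

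Section 9.1 words the frequency hypothesis without that restriction, as a difference in "feeding therapy frequency recommendations when using v. not using the tool". Section 9.4.3 analyses frequency as "3 response categories – 1xweek, 2xweek, less than 1 time per week", case by case. Reporting is descriptive, and a chi-square test is added only if its assumptions are judged to be met. For targets, Section 9.4.3 says percentages of therapists "will be compared among therapists using and not using the tool" and does not name the denominator. Section 9.4.2 is equally silent for specialists.

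Sections 9.3, 9.4.2 and 9.4.3 drop participants with incomplete surveys and do not say how items skipped by branching are treated.

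**The concern.** The frequency comparison selects therapists on an answer given after they have, or have not, used the tool. If the tool moves that answer, as the study hypothesises, the two yes groups can contain different kinds of therapist even when allocation is sound. Because each case is analysed separately, tool and no tool are compared between different people, so no within-person pairing offsets the selection.

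Section 3 gives the aim as finding out whether the tool changes decisions about frequency and targets. A yes-only table cannot separate such a change from the arrival of therapists who would otherwise have said no. The trial could report a shift in frequency that no consistent recommender made, or could miss a real one.

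**Working it through.** **Inputs from the documents.** Sections 6.3 and 9.2 give 14 SLPs and 14 OTs in each of two groups: 14 + 14 = 28 per group and 4 × 14 = 56 in total, which reproduces the stated sample size. Within each case the comparison is therefore 28 v 28 before any restriction to yes. The size was set by funding and balance. The documents give no alpha, power, yes rates or frequency mix.

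**Assumptions.** Two-sided alpha is 0.05. Let p0 and p1 be the yes rates without and with the tool, A the frequency mix of therapists who would say yes either way, and B the mix of those who say yes only with the tool. Nobody moves from yes to no, and no always-yes therapist changes frequency. Mixes are listed as twice a week or more / weekly / less than weekly.

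**Formula.** Mix among yes-sayers with the tool = [p0·A + (p1 − p0)·B] / p1. Without the tool it is A.

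| Assumed mix | p0 to p1 | Top category among yes-sayers | Change |
|---|---|---|---|
| Extreme: A 50/50/0%, B 0/0/100% | 70% to 95% | 50% to 0.35/0.95 = 36.8% | −13.2 points |
| Less extreme: A 40/50/10%, B 0/30/70% | 70% to 90% | 40% to 0.28/0.90 = 31.1% | −8.9 points |
| Same | 90% to 100% | 40% to 36.0% | −4.0 points |
| Same | 95% to 97% | 40% to 0.38/0.97 = 39.2% | −0.8 points |
| Milder: A 40/50/10%, B 10/50/40% | 70% to 90% | 40% to 0.30/0.90 = 33.3% | −6.7 points |
| B equal to A | any | unchanged | 0 |

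These are illustrations, not bounds.

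**Masking.** In the less extreme mix at 70% to 90%, suppose the tool truly raised the top-category share of always-yes therapists to x. The yes-only table would show no change when 0.70x/0.90 = 0.40, that is x = 0.514. A real rise from 40% to about 51% would be hidden.

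**The chi-square test.** In 20,000 simulated trials of the extreme case, the three-category test rejects in about 64% if it is always run. The plan runs it only if assumptions hold, and does not define them. Expected yes counts are 28 × 0.70 = 19.6 and 28 × 0.95 = 26.6, with 28 × 0.25 = 7.0 answers of less than weekly. Expected counts in those two cells are 7.0 × 19.6/46.2 = 3.0 and 7.0 × 26.6/46.2 = 4.0, so 2 of 6 cells fall below 5.

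- If at least 80% of expected counts must be 5 or more and none below 1, a test that is both permitted and significant occurs in about 21% of trials.
- If every expected count must be at least 5, it occurs in about 3%.
- In the less extreme mix at 70% to 90%, the figures are about 15% with the test always run and 6% under the first rule.

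**All therapists as denominator.** For the less extreme mix at 70% to 90%, the four levels (the three above, then no therapy) are 28/35/7/30% without the tool and 28/41/21/10% with it. The top share stays at 28%, and the movement appears where it happened.

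In the extreme case the four levels are 35/35/0/30% and 35/35/25/5%. Pearson chi-square on these rejects in about 93% of trials, because it picks up the therapy decision. A rank test rejects in about 8%.

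**Targets.** Assume a target is chosen by 60% of always-yes and 20% of newly-yes therapists, with yes rates of 70% and 90%. Among yes-sayers it goes from 60% to (0.70 × 0.60 + 0.20 × 0.20)/0.90 = 51%, a fall. Among all therapists it goes from 0.70 × 0.60 = 42% to 0.42 + 0.04 = 46%, a rise. The direction depends on the denominator that the plan does not state.

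**The case against.** The strongest case on the other side has four parts.

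- **The yes rate may hardly move.** The checklist in Section 6.1.1 prompts referral on top of the therapist's own treatment, which presupposes therapy, and the synopsis hypothesis names only referral. This limits the likely size. It does not remove the problem, because Sections 4.1 and 9.1 do hypothesise a change in therapy recommendations.
- **Readers can see any shift.** The yes/no result is reported by case as a primary endpoint. That stands, but nothing in the plan links it to the frequency table.
- **Frequency is undefined after a no.** A yes-only description, labelled conditional and shown with yes counts, is defensible. The plan does not label it so, and its hypothesis is worded for therapists' recommendations in general.
- **These are secondary, mainly descriptive endpoints in a pilot.** That stands and sets the weight of the point.

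Three stronger readings are tempting. A reader might infer that restricting to yes-sayers must distort the comparison; it does so only if the yes rate changes and the newly-yes therapists differ. A reader might infer a false frequency finding in about 64% of trials; that figure needs the extreme mix and ignores the plan's own condition on running the test. A reader might infer that targets and specialists are also compared only among yes-sayers; the items are asked only after a yes, but the percentages could be of all therapists.

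**Conclusion.** The concern holds firmly for frequency. The planned comparison conditions on a post-assignment answer that is itself a primary endpoint the tool is hypothesised to change, and nothing elsewhere in the plan deals with it. The two yes groups may not be comparable, and a shift in who says yes can look like or mask a shift in frequency.

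The size rests wholly on assumed rates. The apparent fall in the top category is about 13 points in an extreme case (yes rate 70% to 95%), about 9 points (70% to 90%) and 4 points (90% to 100%) with a less extreme mix, and about 1 point at 95% to 97%. The descriptive percentages carry this distortion whether or not a test is run. A permitted and significant chi-square would occur in about 3% to 21% of trials in the extreme case, under common expected-count rules.

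For targets and specialists the supportable point is narrower: the denominator is unstated, and the direction of the result can depend on it. The effect is on interpretation of secondary results and of the specialist percentages. It does not touch the two yes/no primary comparisons.

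**What to change.** In Sections 9.4.2 and 9.4.3, for each case:

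1. Report frequency for all analysed therapists per condition (up to 28 v 28), with no therapy recommended as the lowest of four ordered levels.
2. If a test is run, name an ordinal rank test, for example Mann-Whitney. Do not use Pearson chi-square on four levels, which would mostly repeat the primary therapy result.
3. Give targets and specialists as a percentage of all analysed therapists per condition, counting a no to therapy or to referral as not chosen.
4. Keep the yes-only tables as descriptive support, labelled conditional, with the number of yes answers shown in each condition.
5. State that items skipped after a no are not missing under the complete-survey rule. Read literally, that rule could remove every therapist who answered no.

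The cost is wording only; no new data or survey change is needed. The downside is that the four-level result combines the therapy decision with frequency, which the yes-only table beside it separates.

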## 4 STUDY DESIGN

### 4.1 OVERALL DESIGN

This is a randomized crossover pilot study. It will be conducted online through one site, UNC Chapel Hill. The study intervention is the 'Clinical Feeding Tool' also known as the decision support tool. Our hypothesis is that clinicians will change their recommendations for feeding therapy and specialist referral when using the tool compared to when they do not use the tool. Clinicians will be randomly assigned to respond to either Case A or Case B without using the tool (2 groups). Then, they will respond to the other case using the tool. Total participation time is estimated at 20 minutes.

### 4.2 SCIENTIFIC RATIONALE FOR STUDY DESIGN

We have selected a crossover design for this pilot study in order to directly compare use of the tool to no use of the tool among a small group of participants. Therefore, participants will serve as their own control group. This was chosen given the varying experience of the participants with feeding.

### 4.3 JUSTIFICATION FOR DOSE

All therapists will view the full tool in the survey in order to directly compare use of the tool to no use of the tool.

### 4.4 END OF STUDY DEFINITION

A participant is considered to have completed the study if he or she has completed the survey.

## 5 STUDY POPULATION

### 5.1 INCLUSION CRITERIA

In order to be eligible to participate in this study, an individual must meet all of the following criteria:

1. Provision of signed and dated informed consent form
2. Stated willingness to comply with all study procedures and availability for the duration of the study
3. Male or female, aged 18 or older
4. Speech language pathologist or occupational therapist

5. At least 2 years of experience evaluating and treating pediatric feeding
6. Have worked in Early Intervention in the last 5 years
7. English proficiency
8. Currently reside in NC

## 5.2 EXCLUSION CRITERIA

An individual who meets any of the following criteria will be excluded from participation in this study:

1. Less than 2 years of experience
2. Have not worked in Early Intervention in the last 5 years
3. Does not currently reside in NC

## 5.3 LIFESTYLE CONSIDERATIONS

Not applicable

## 5.4 SCREEN FAILURES

Screen failures are defined as participants who express interest in participating in the clinical trial but are not subsequently randomly assigned to the study intervention or entered in the study. A minimal set of screen failure information is required to ensure transparent reporting of screen failure participants, to meet the Consolidated Standards of Reporting Trials (CONSORT) publishing requirements and to respond to queries from regulatory authorities. Minimal information includes screen failure details, eligibility criteria, and any serious adverse event (SAE).

